## **I. Hypotheses and Specific Aims**

**Aim 1.** Evaluate the efficacy of the Cogito Companion as an upstream suicide prevention intervention.

**Hypothesis 1.1.** Participants allocated to the Cogito Companion will report significantly fewer episodes of distress and less distress over the course of the study (Outcome Questionnaire-45; OQ-45) compared to those allocated to the Active Control group.

**Hypothesis 1.2.** Among those with episodes of clinically meaningful distress, those allocated to the Cogito Companion will more rapidly engage in treatment (medical record review and Client Services Receipt Inventory-EU-Revised; CSRI-EU-R) to address such symptoms versus those allocated to the Active Control group.

**Hypothesis 1.3.** Participants allocated to the Cogito Companion will report significantly fewer episodes of and less severe depressive (Patient Health Questionnaire-9; PHQ-9) and post-traumatic symptoms (Post Traumatic Stress Disorder Checklist-5; PCL-5), and suicide-related thoughts (Beck Scale for Suicide Ideation; BSS, Columbia-Suicide Severity Rating Scale Screener; C-SSRS Screener), as well as overall increased perceived physical/psychological health functioning (Rand 36-Item Health Survey; SF-36) over the course of the study compared to those allocated to the Active Control condition.

**Aim 2.** Evaluate the acceptability and feasibility of the Cogito Companion among military personnel (Sailors).

**Aim 2.1.** Acceptability of Cogito Companion will evaluate based on participant satisfaction (CSQ), participant engagement in application-related activities (e.g., leaving voice recordings), and time spent on the application. Acceptability refers to the suitability of an intervention from the perspectives of the participants.

**Aim 2.2.** Feasibility of Cogito Companion will be evaluated based on participant retention and accrual, and number and type (minor, moderate, severe) of technical challenges noted during implementation. Feasibility refers to the ease of implementation.

**Exploratory Aim.** Identify patterns of distress, depressive symptoms, post-traumatic symptoms, suicide-related thoughts, and perceived physical and psychological health functioning over the course of the study among the entire sample, as well as within the Cogito Companion and Active Control groups.

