## F. Data Analysis Plan

**Power Analysis.** Power is calculated for the two primary hypotheses assessing episodes of distress and distress over the course of the study. We will recruit 1418 participants and expect approximately 33% to decline participation resulting in 950 participants randomized to either the Cogito Companion or Active Control groups, stratified by gender, force and phone type. Assuming 21% attrition, it is expected that 750 participants will complete the entire protocol. While the analysis will include all participants who are randomized, power is based on 750 completed (375 per group). Power to address episodes of distress was estimated using the Poisson regression procedure in Power and Sample Size (PASS) v13. An episode of distress is defined as an OQ-45 total score of  $\geq 64$  with each participant having a maximum of 6 possible episodes (every 2 weeks for weeks 2-12 of the study, inclusive). We wish to detect a 15% difference in the number of episodes of distress over the 3-month study period, and we assume a two-sided test and a significance level of 0.025 to control for the two primary tests (number of episodes and overall distress). If the Active Control mean response rate is 3.5 (i.e., number of episodes in the 3-month study period) we will have 97% power to detect a 15% difference. For Active Control response rates of 3, 2.5, 2 and 1.5, power is then 94%, 89%, 81% and 68%, respectively. For the second primary hypothesis, we will calculate the Area Under the Curve (AUC) using an estimate statement within a linear mixed model described below. We wish to demonstrate that the Cogito Companion is superior to Active Control by a margin of at least 14 points (minimally clinically significant difference, translates to an AUC difference of 84). Using the Superiority by a Margin procedure in PASS v13, 375 participants per group provides 90% power to demonstrate superiority, assuming a true difference of  $\geq 18.7$  points (AUC difference of 112.2) with a significance level of 0.025.

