**Analysis Plan.** All analyses will assume a two-sided test of hypothesis, a significance level of 0.05 (unless otherwise indicated) and will be run in SAS v9.4 or higher, or R v3.3 or higher. To check randomization, demographic and clinical characteristics will be compared between groups using t-tests, chi-square tests or nonparametric tests, as appropriate. If any variable is found to be significantly different between the groups and is also plausibly associated with an outcome, it will be considered as potential confounders in the models described below.

**Aim 1.** To address the hypothesis regarding episodes of distress first using Poisson regression will be used to model the number (response rate) of episodes of distress as a function of group (0=Active Control, 1=Cogito), any potential confounders, and an offset of log (time) to account for varying lengths of follow-up. If the deviance is estimated to be  $> 1.5$ , Negative Binomial regression will be used instead, incorporating the same variables. The parameter estimate associated with the group variable will be exponentiated, providing an estimate of the ratio of response rates between the groups and will be reported with a 97.5% confidence interval (CI). To address the hypothesis regarding distress over the course of the study, a linear mixed-effects model will be employed with longitudinal OQ-45 scores as the dependent variable and group, potential confounders, and an interaction between group and time (using either natural cubic B-spline transformations on time or polynomial transformations on time) as independent variables. These transformations will also be applied to the random time effects so that individual trajectories can be calculated. Akaike's Information Criterion will be used to determine which model provides the best fit (both between the B-spline/polynomial models and within them). Once a final model is determined, the difference in AUC will be calculated and between groups and compared to the clinically meaningful AUC difference of 84 using a one-sided test. Here the null hypothesis is that  $AUC_{AC} - AUC_{Cogito} \geq 84$ , and the alternative hypothesis is that  $AUC_{AC} - AUC_{Cogito} < 84$ . The estimated difference will be reported with the one-sided 97.5% CI. For hypothesis 1.2, a Kaplan-Meier estimate will be used to compare the median time to treatment engagement

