between the groups and each median will be reported with 95% CIs. Treatment engagement is operationalized as a visit with any medical or mental health provider in which a mental health related ICD code is identified. and will be determined by medical record review. Additionally, the total number of mental health visits calculated from the CSRI-EU-R will be modeled using a Poisson or Negative Binomial regression model to estimate the difference in number of visits between the groups over the course of the study. The model will be set up similarly to the OQ-45 model. Hypothesis 1.3 is similar to hypothesis 1.1 such that we wish to look at episodes of depressive symptoms (PHQ-9), post-traumatic symptoms (PCL-5) and suicide-related thoughts (BSS) as well as severity of each over the course of the study. We also wish to look at perceived physical and psychological health functioning (RAND SF-36) over the course of the study. The methods employed to address hypothesis 1.1 will be utilized to estimate the difference in number of episodes of each outcome (excluding the SF-36) as well as the difference in AUC for each outcome. Zero-inflated negative binomial regression will be considered for the BSS if a large proportion of the participants do not exhibit suicidal thoughts and transformations will be considered for the AUC BSS analysis, given that it is likely to be highly skewed. Cutoffs for episodes of depressive/post traumatic symptoms, and suicidal thoughts are  $\geq 10$  (PHQ-9),  $\geq 33$  (PCL-5), and  $\geq 2$  (BSS), respectively.

***Aim 2.*** We will assess the proportion of participants who find the Cogito Companion acceptable, defined as  $\geq 70\%$  of participants scoring  $\geq 24$  on the CSQ. The proportion of Cogito Companion participants with a CSQ score of  $\geq 24$  will be calculated with a 95% CI. Additionally, the proportion of participants engaging in activities will be reported with a 95% CI as well as the median (range) amount of time spent on the application. Feasibility will be measured by the proportion of Cogito Companion participants who complete treatment and reasons for termination will be examined.

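### If a zero-inflated model is fitted to BSS episodes, the planned exponentiated group term is not the rate ratio over all allocated participants and can understate a preventive effect

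*Protocol*

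**What the plan says.** Hypothesis 1.3 (Protocol, section I) is framed by allocation. It begins "Participants allocated to the Cogito Companion will report significantly fewer episodes of and less severe depressive" symptoms and goes on to post-traumatic symptoms and suicide-related thoughts. It is not restricted to people who already have such thoughts.

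For the analysis, section F says: "The methods employed to address hypothesis 1.1 will be utilized to estimate the difference in number of episodes of each outcome". Under Hypothesis 1.1 that method is Poisson regression, or negative binomial if overdispersed, with a stated output: "The parameter estimate associated with the group variable will be exponentiated, providing an estimate of the ratio of response rates between the groups". For the BSS, where an episode is a score of 2 or more, section F adds: "Zero-inflated negative binomial regression will be considered for the BSS if a large proportion of the participants do not exhibit suicidal thoughts".

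The plan gives no numeric trigger for the switch. It does not say whether group enters the zero part, whether a zero-part effect is reported, or how the two parts would be combined. The SAP reproduces this text under its original plan and says the team kept to that plan after the aims were revised. The revised aims mention the BSS only in the exploratory aim.

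**The concern.** In a Poisson or ordinary negative binomial model, the exponentiated group term is the ratio of mean episodes between the arms, so the stated reading is correct. A zero-inflated negative binomial has two parts: a probability of belonging to a class that never has an episode, and a count model for everyone else. The group term in the count part compares arms only within that second, unobserved class, and the intervention can change who belongs to it.

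The background section sets out an upstream aim of stopping personnel from ever reaching suicidal thoughts. An effect of that kind falls largely in the zero part, which the inherited rule does not mention. The published ratio for suicidal-thought episodes could then sit closer to 1 than the randomised effect, while still being labelled a rate ratio.

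**Working it through.** **Inputs from the documents.** There are at most six biweekly assessments ("every 2 weeks for weeks 2-12 of the study, inclusive", stated for the OQ-45; the BSS is also biweekly in Table 1). For sample size, "power is based on 750 completed (375 per group". The primary tests use two-sided 0.025. No BSS prevalence or BSS power figure is given.

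**Step 1: the plan's own figure.** The nearest stated figure is the Poisson power for a 15% difference in OQ-45 episodes. With N = 750, equal arms and ratio RR = 0.85:

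power = Φ{[√(N·μ·(ln RR)²) − z·√V0] / √V1}, where z = 2.241, V0 = 1/(0.5 × 0.5) = 4 and V1 = 1/0.5 + 1/(0.5 × 0.85) = 4.353.

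For μ = 3.5: √(750 × 3.5 × 0.02641) = 8.327; (8.327 − 4.483)/2.086 = 1.84; Φ = 96.7%. Control rates of 3, 2.5, 2 and 1.5 give 93.9%, 89.0%, 80.7% and 67.9%. The plan states 97%, 94%, 89%, 81% and 68%, so its figures reproduce. The ratio used there is a ratio of arm means over all participants.

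**Step 2: the identity.** Let π0 and π1 be the structural-zero shares in control and app arms, and β the count-part group coefficient. Then

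overall mean ratio = [(1 − π1)/(1 − π0)] × exp(β).

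So exp(β) equals the overall ratio only if the app leaves the at-risk share unchanged. Holding the overall ratio at 0.75:
- at-risk share ratio 1.00: exp(β) = 0.75
- at-risk share ratio 0.875: exp(β) = 0.75/0.875 = 0.857
- at-risk share ratio 0.75: exp(β) = 1.00

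**Step 3: large-sample illustration (assumed inputs).** Assume 20% of controls and 15% of app users are at risk, with a mean of about 2.5 positive screens among them in both arms, capped at 6. The true ratio is 0.15/0.20 = 0.75. In 120,000 simulated people the observed mean ratio was 0.745. The count-part ratio was 1.01 with group in both parts and 0.97 with group in the count part only. The zero-part odds ratio was 1.44, against (0.85/0.15)/(0.80/0.20) = 1.42 expected. A separate refit gave 1.00 and 0.97 against a sample ratio of 0.74.

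**Step 4: trial-size simulation (assumed inputs).** 375 per arm, 200 trials per row, at-risk mean 2.5 in both arms, and the app acting only on the at-risk share. Cells show the median estimate and the share of trials rejecting at two-sided 0.025.

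| Counts | π0, π1 | True ratio | Count part, group in both | Zero-part odds ratio, group in both | Count part, group there only | Ordinary negative binomial |
|---|---|---|---|---|---|---|
| Negative binomial | 0.70, 0.85 | 0.50 | 0.99 (4%) | 2.44 (98%) | 0.76 (22%) | 0.49 (80.5%) |
| Negative binomial | 0.80, 0.90 | 0.50 | 0.99 (3.5%) | 2.33 (83.5%) | 0.79 (18.5%) | 0.50 (57%) |
| Negative binomial | 0.60, 0.72 | 0.70 | 1.00 (2%) | 1.67 (71%) | 0.88 (11%) | 0.705 (36%) |
| Bounded 0–6 | 0.70, 0.85 | 0.50 | 1.01 (2%) | 2.35 (99.5%) | 0.94 (4%) | 0.51 (85%) |
| Bounded 0–6 | 0.80, 0.90 | 0.50 | 0.99 (2.5%) | 2.24 (90.5%) | 0.92 (5%) | 0.48 (62.5%) |
| Bounded 0–6 | 0.60, 0.72 | 0.70 | 1.00 (0.5%) | 1.65 (76.5%) | 0.97 (4.5%) | 0.72 (41%) |

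With group in both parts, the count-part test rejects at about its nominal 2.5% although episodes truly fall by 50% or 30%. With group in the count part only, the ratio is attenuated. The ordinary negative binomial recovers the overall ratio.

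**The case against.** The strongest reply is that the fault lies in silence. The exponentiation sentence was written for Poisson and negative binomial models of OQ-45 episodes, and the zero-inflated model is a possible departure that is only to be considered. Nothing says the zero part would go unreported, and with group in both parts the benefit is visible in the same output. This stands, and it limits the point to what the inherited rule would give if applied literally. It does not remove the point, because that rule is the only output the plan specifies.

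A reader might infer that the plan would declare an effective app to have no effect. The documents do not support that. A ratio of 1 needs an app that acts only on the at-risk share. If the app also reduces repeat positive screens, the count part shows it, and with group in the count part only the medians above run from 0.76 to 0.97. The plan also has a separate BSS area-under-the-curve comparison that could show a benefit.

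A reader might also infer that the zero-inflated model is likely to be used. The eligibility criteria do not select on symptoms and section F expects BSS skew, so many zeros are plausible. But no prevalence is given, so the likelihood cannot be stated.

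Finally, the remedy corrects the estimate more than the chance of a significant result. Under the Step 3 assumptions at 375 per arm, a robust single-part ratio had a median of 0.75 but was significant in only about 19% of simulated trials at 0.025 and 29% at 0.05. This also stands.

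**Conclusion.** The point holds in a limited form. If the zero-inflated model is chosen and the Hypothesis 1.1 rule is applied to its count part, the reported figure is not the ratio of episode rates over all allocated participants. A preventive benefit is then attenuated towards 1, and lost only in the limiting case. The identity is exact. The sizes (0.75 reported as about 0.97 to 1.0; 0.50 or 0.70 reported as 0.76 to 1.01) rest on assumed at-risk shares, an assumed at-risk mean of 2.5, and an app that acts only on the at-risk share.

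The priority is minor. Hypothesis 1.3 is not one of the two primary hypotheses, and the revised aims keep the BSS only as exploratory. The text still matters because the SAP says the original plan was followed.

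**What to change.** In Hypothesis 1.3 of section F, and in the matching SAP text, define the BSS episode effect as the ratio of mean positive screens over all randomised participants, with its confidence interval. Either of two routes would do:
- a single-part log-link model with robust standard errors; or
- if a zero-inflated model is fitted, group in both parts, both parts reported, and the two combined into a marginal mean ratio with a delta-method or bootstrap interval.

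In either case, report the arm difference in the proportion with any BSS score of 2 or more, and do not label the count-part coefficient a rate ratio. There is no need to ban the zero-inflated model, but its trigger should be stated. State the interval level as well, since section F leaves open whether 97.5% carries over to Hypothesis 1.3.

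The cost is a few sentences of SAP wording and possibly a slightly wider interval than a model-based one. No new data are needed.

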## **G. Summarize Knowledge to be Gained**

Establishing the efficacy of the Cogito Companion has direct military relevance aligned with Leadership's desire to promote wellness and help-seeking behaviors, as well as prevent suicide-related behaviors among Naval personnel during the redeployment home following a stressful forward operating mission. Importantly, this upstream intervention (the Cogito Companion) has the potential to facilitate identification of those transitioning (e.g., redeployment, permanent change of station, separation) whose risk may: 1) not be easily identified immediately post-deployment; 2) and/or may increase secondary to intra- and inter-personal stressors during the reintegration period. Identifying and engaging such individuals in treatment using traditional methods has proven to be challenging. Based on consumer preferences, technology is finding its way into the health arena. Identifying means by which technology can be used to evaluate risk identification is imperative. Specifically, evidence-based, portable, and non-pathologizing interventions, which capitalize on Active Duty Service Member comfort with technology, are necessary to prevent suicide among members of this high-risk cohort. Importantly, project aims also align with the MSRC objective of "fund[ing] ... clinical trial ... research with high value to the MSRC," aimed at promoting help-seeking behavior and preventing suicide.

NCT 04159480 Study Analysis Plan
Facilitating Assessment of At-Risk Sailors Using Technology (FAAST)
VA Eastern Colorado Health Care System
29 May 2023

Originally, members of the team obtained funding to conduct a randomized controlled trial (RCT) to test the efficacy of Cogito versus active control among Navy personnel; however, significant implementation challenges arose secondary to the COVID-19 pandemic. Thus, with permission from the study sponsor, aims were in part revised as follows: 1) evaluate the feasibility (application download/use and technical challenges) and acceptability (satisfaction) of the Cogito among a cohort of naval personnel; 2) longitudinally characterize time to risk identification by cohort (Cogito/Active Control); 3) identify patterns of symptoms (distress, depressive, post traumatic, suicide-related thoughts and mental and physical health functioning) over time and by study group. However, while the aims of the study changed, the team continued to follow Power Analysis and the original analysis plan. Please see the two sections provided below for greater insight into the changes. Grant funds were used to purchase the use of the Cogito Application for this study. The application is not available for general use, and other than providing technical support, the Cogito Team was not involved with data collection or analyses.

Original statistical analysis plan (SAP) from the protocol:

“Power Analysis. Power is calculated for the two primary hypotheses assessing episodes of distress and distress over the course of the study. We will recruit 1418 participants and expect approximately 33% to decline participation resulting in 950 participants randomized to either the Cogito Companion or Active Control groups, stratified by gender, force and phone type. Assuming 21% attrition, it is expected that 750 participants will complete the entire protocol. While the analysis will include all participants who are randomized, power is based on 750 completed (375 per group). Power to address episodes of distress was estimated using the Poisson regression procedure in Power and Sample Size (PASS) v13. An episode of distress is defined as an OQ-45 total score of ≥ 64 with each participant having a maximum of 6 possible episodes (every 2 weeks for weeks 2-12 of the study, inclusive). We wish to detect a 15% difference in the number of episodes of distress over the 3-month study period, and we assume a two-sided test and a significance level of 0.025 to control for the two primary tests (number of episodes and overall distress). If the Active Control mean response rate is 3.5 (i.e., number of episodes in the 3-month study period) we will have 97% power to detect a 15% difference. For Active Control response rates of 3, 2.5, 2 and 1.5, power is then 94%, 89%, 81% and 68%, respectively. For the second primary hypothesis, we will calculate the Area Under the Curve (AUC) using an estimate statement within a linear mixed model described below. We wish to demonstrate that the Cogito Companion is superior to Active Control by a margin of at least 14 points (minimally clinically significant difference, translates to an AUC difference of 84). Using the Superiority by a Margin procedure in PASS v13, 375 participants per group provides 90% power to demonstrate superiority, assuming a true difference of ≥ 18.7 points (AUC difference of 112.2) with a significance level of 0.025.

Analysis Plan. All analyses will assume a two-sided test of hypothesis, a significance level of 0.05 (unless otherwise indicated) and will be run in SAS v9.4 or higher, or R v3.3 or higher. To check randomization, demographic and clinical characteristics will be compared between groups using t-tests, chi-square tests or nonparametric tests, as appropriate. If any variable is found to be significantly different between the groups and is also plausibly associated with an outcome, it will be considered as potential confounders in the models described below.

Aim 1. To address the hypothesis regarding episodes of distress first using Poisson regression will be used to model the number (response rate) of episodes of distress as a function of group (0=Active Control, 1=Cogito), any potential confounders, and an offset of log (time) to account for varying lengths of follow-up. If the deviance is estimated to be > 1.5 , Negative Binomial regression will be used instead, incorporating the same variables. The parameter estimate associated with the group variable will be exponentiated, providing an estimate of the ratio of response rates between the groups and will be reported with a 97.5% confidence interval (CI). To address the hypothesis regarding distress over the course of the study, a linear mixed-effects model will be employed with longitudinal OQ-45 scores as the dependent variable and group, potential confounders, and an interaction between group and time (using either natural cubic B-spline transformations on time or polynomial transformations on time) as independent variables. These transformations will also be applied to the random time effects so that individual trajectories can be calculated. Akaike’s Information Criterion will be used to determine which model provides the best fit (both between the B-spline/polynomial models and within them). Once a final

model is determined, the difference in AUC will be calculated and between groups and compared to the clinically meaningful AUC difference of 84 using a one-sided test. Here the null hypothesis is that $AUC_{AC} - AUC_{Cogito} \geq 84$, and the alternative hypothesis is that $AUC_{AC} - AUC_{Cogito} < 84$. The estimated difference will be reported with the one-sided 97.5% CI. For hypothesis 1.2, a Kaplan-Meier estimate will be used to compare the median time to treatment engagement between the groups and each median will be reported with 95% CIs. Treatment engagement is operationalized as a visit with any medical or mental health provider in which a mental health related ICD code is identified. and will be determined by medical record review. Additionally, the total number of mental health visits calculated from the CSRI-EU-R will be modeled using a Poisson or Negative Binomial regression model to estimate the difference in number of visits between the groups over the course of the study. The model will be set up similarly to the OQ-45 model. Hypothesis 1.3 is similar to hypothesis 1.1 such that we wish to look at episodes of depressive symptoms (PHQ-9), post-traumatic symptoms (PCL-5) and suicide-related thoughts (BSS) as well as severity of each over the course of the study. We also wish to look at perceived physical and psychological health functioning (RAND SF-36) over the course of the study. The methods employed to address hypothesis 1.1 will be utilized to estimate the difference in number of episodes of each outcome (excluding the SF-36) as well as the difference in AUC for each outcome. Zero-inflated negative binomial regression will be considered for the BSS if a large proportion of the participants do not exhibit suicidal thoughts and transformations will be considered for the AUC BSS analysis, given that it is likely to be highly skewed. Cutoffs for episodes of depressive/post traumatic symptoms, and suicidal thoughts are ≥ 10 (PHQ-9),⁴⁵ ≥ 33 (PCL-5),⁴⁶ and ≥ 2 (BSS),⁴⁷ respectively.

Aim 2. We will assess the proportion of participants who find the Cogito Companion acceptable, defined as $\geq 70\%$ of participants scoring ≥ 24 on the CSQ. The proportion of Cogito Companion participants with a CSQ score of ≥ 24 will be calculated with a 95% CI. Additionally, the proportion of participants engaging in activities will be reported with a 95% CI as well as the median (range) amount of time spent on the application. Feasibility will be measured by the proportion of Cogito Companion participants who complete treatment and reasons for termination will be examined.

Exploratory Aim. To explore patterns of distress experienced by participants over the course of the study, individual OQ-45 curves modeled in Aim 1 will be qualitatively clustered into groups based on visual inspection of the trajectory patterns. Once distinct patterns are identified and labeled, baseline demographic and clinical characteristics of participants in each pattern will be summarized and reported. This will be performed for the entire sample, as well as within each group. This is considered a hypothesis generating aim. This analysis will be repeated for the PHQ-9, PCL-5, BSS and SF-36.”

Revised and approved aims of the new statistical analysis plan:

Aim 1 (Revised - 2022). Longitudinally characterize risk by cohort (Active Control – study measures pushed only; Cogito Companion – study measures pushed plus Cogito Companion application [includes feedback from passive monitoring models]). Hypothesis 1.1 First characterization of risk, post-model score availability (7 days after download of app for model scores, 14 days for stability), will occur more quickly for the Cogito Companion group.

Aim 2. Evaluate the acceptability and feasibility of the Cogito Companion among military personnel. Aim 2.1. Acceptability of Cogito Companion will be evaluated based on participant satisfaction, participant engagement in application-related activities, and time spent on the application. Aim 2.2. Feasibility of Cogito Companion will be evaluated based on participant retention and accrual, and number and type of technical challenges noted during implementation.

Exploratory Aim. Identify patterns of distress (OQ-45), depressive symptoms (PHQ-9), post-traumatic symptoms (PCL-5), suicide-related thoughts (BSS; CSSRS Screener), and perceived physical and psychological health functioning (SF-36) over the course of the study among the entire sample, as well as within the Cogito Companion and Active Control groups.”

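### The OQ-45 AUC hypotheses are reversed: superiority by the 84-unit margin sits in the null, so the stated test cannot establish it

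*SAP*

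**What the plan says.** Hypothesis 1.1 (Protocol, I. Hypotheses and Specific Aims) expects that Cogito participants "will report significantly fewer episodes of distress and less distress over the course of the study". An episode of distress is an OQ-45 total of 64 or more, so higher scores are worse and benefit is a positive AUC_AC − AUC_Cogito.

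The Power Analysis (Protocol, F. Data Analysis Plan) states the aim: "We wish to demonstrate that the Cogito Companion is superior to Active Control by a margin of at least 14 points". It converts the margin to 84 AUC units and uses a superiority-by-a-margin procedure. The SAP's reprint says that "375 participants per group provides 90% power to demonstrate superiority", at an assumed true difference of 18.7 points (AUC 112.2) and a significance level of 0.025.

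Under Aim 1 of the same section, the AUC difference is to be "compared to the clinically meaningful AUC difference of 84 using a one-sided test". The null is then given as AUC_AC − AUC_Cogito ≥ 84, and "the alternative hypothesis is that $AUC_{AC} - AUC_{Cogito} < 84". The SAP's reprint has the same inequalities. For the interval, "The estimated difference will be reported with the one-sided 97.5% CI"; the side is not named.

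The SAP's introduction says that, although the aims changed, "the team continued to follow Power Analysis and the original analysis plan". The revised aims mention OQ-45 only under the Exploratory Aim: "Identify patterns of distress (OQ-45), depressive symptoms (PHQ-9), post-traumatic symptoms (PCL-5").

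**The concern.** A test supports a claim by rejecting the null. The claim the trial was sized for, a difference of at least 84 in favour of Cogito, is here the null itself. Rejection would show only that the difference is below 84, which is what one expects if the app does nothing. Failure to reject would not show superiority either.

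Anyone who programs the test from this text would use the wrong tail. Because the interval's side is not named, they could also report the upper bound, which matches the written alternative but says nothing about superiority. The methods for Hypothesis 1.1 are reused for the AUC analyses under Hypothesis 1.3, so the unclear direction could carry over to those.

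**Working it through.** **Inputs from the documents:** margin 14 points = 84 AUC units; assumed true difference 18.7 points = 112.2 AUC units; 375 per group; 90% power; significance level 0.025, taken as one-sided to match the one-sided test and one-sided 97.5% interval.

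**Scale check:** 14 × 6 = 84 and 18.7 × 6 = 112.2, so both conversions agree.

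**Stated power:** neither document gives an SD, so the 90% cannot be reproduced independently. Under a two-sample normal approximation, the SD it implies is

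SD = (18.7 − 14) / [(1.960 + 1.2816) × √(2/375)] = 19.85 points

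SE of the AUC difference = 6 × 19.85 × √(2/375) = 8.70

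**Rejection probabilities at true difference d:**

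- As written (reject for low values): Φ((84 − d)/SE − 1.96)
- Corrected (reject for high values): Φ((d − 84)/SE − 1.96)

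| True AUC difference | As written | Corrected |
|---|---|---|
| 0 (no effect) | about 1 | about 0 |
| 42 (half the margin) | 0.998 | about 0 |
| 84 (margin) | 0.025 | 0.025 |
| 112.2 (design value) | about 1 × 10⁻⁷ | 0.90 |

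The 0.90 holds by construction, because the SD was solved from it. It shows that the stated power belongs to the corrected hypotheses and not to the written ones.

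**Sensitivity to the missing SD (test as written):**

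| Assumed SD (points) | SE | Reject at d = 0 | Reject at d = 112.2 |
|---|---|---|---|
| 15 | 6.57 | about 1 | 2 × 10⁻¹⁰ |
| 25 | 10.95 | about 1 | 3 × 10⁻⁶ |
| 30 | 13.15 | 0.999995 | 2 × 10⁻⁵ |

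If 0.025 were two-sided, the implied SD would be about 18.3 points, and rejection at 112.2 would be about 4 × 10⁻⁹.

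**Failing to reject does not help.** With SE 8.70, the written null is retained for any estimate above 84 − 1.96 × 8.70 = 66.9. That range includes estimates below the margin.

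**Side of the interval.** At an estimate of 112.2, the bounds are 112.2 ∓ 1.96 × 8.70. The lower bound, 95.1, is above 84 and shows superiority by the margin. The upper bound, 129.3, shows nothing about it.

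**The case against.** The strongest reply is that this is a drafting slip with little remaining effect. The power section fixes the intended direction, so a careful analyst would probably run the right test, and the unnamed bound might turn out to be the lower one. The faulty text in the SAP is a quotation of the original plan. The revised Hypothesis 1.1 concerns time to first characterization of risk, and no revised aim claims superiority on OQ-45 AUC.

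Much of this is fair. A slip is the likeliest explanation, and the documents do not establish that the test still supports a confirmatory claim. Rejection at zero effect is also not a type I error: the written alternative is then true, and a false efficacy claim would need someone to read rejection as superiority. The very small probabilities are orders of magnitude only. They rest on an inferred SD and a two-sample approximation with completers, whereas the plan specifies a mixed model in all randomized participants.

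None of it removes the contradiction. The inequalities are the same in both documents, and no passage states them the other way round. The conflict lies within one version of the plan, between its power and analysis sections, so it is not a difference between old and revised text. The SAP also says that the original analysis plan was still followed.

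**Conclusion.** The concern holds. The decision rule for an outcome that the Protocol names as one of two primary hypotheses cannot deliver the conclusion the trial was powered for. This follows from the direction of the scale and the two inequalities alone. The size figures (rejection about 1 at no effect and about 10⁻⁷ at the design effect) assume the SD implied by the stated power, 375 per arm and one-sided 0.025. The pattern is unchanged for SDs of 15 to 30 points. The practical consequence depends on a status the SAP leaves unclear: serious if the test is still primary, smaller if it is exploratory. The text needs correction in either case.

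**What to change.** - **Hypotheses:** in the Protocol, write H0: AUC_AC − AUC_Cogito ≤ 84 and H1: AUC_AC − AUC_Cogito > 84, one-sided at 0.025.
- **Decision rule:** conclude superiority by the margin only if the lower one-sided 97.5% confidence bound exceeds 84, and name that side in the text.
- **SAP:** because the passage there is a quotation, add a dated correction note and leave the quoted text as it stands. The SAP is dated 29 May 2023 and describes the work partly in the past tense, so the note should say whether the correction came before or after the outcome data were seen.
- **Status:** add one sentence saying whether this test remained primary or became exploratory after the 2022 revision.

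The cost is wording and disclosure of timing. The data, margin, estimand, sample size and significance level stay as they are, and participants are not affected.
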